## **12.5 Secondary Aim 2**

To evaluate, from the health system perspective, the cost of implementing EIMG, employing variation from the step-wedge design to estimate the effect of EIMG vs. standard care on costs and outcomes (effectiveness). These estimates will be used to obtain the incremental cost-effectiveness of EIMG vs. standard of care.

*Hypothesis 2: Patients receiving an EIMG referral and participating in the 12-week, community-based PA program will experience improved health outcomes, decreased healthcare service utilization, and a reduction in health care expenditures compared to patients that do not receive an EIMG referral and the opportunity to participate in the PA program.*

[figure not shown]
### **12.5.1 Study Observations.**

The first observed visit for each patient with an EIMG-eligible diagnosis will be designated the index visit date for “candidate” care episodes within each study period. To ensure consistent episodes across periods, candidate episodes will be excluded if the index date is within 90 of the end of a previous care episode for that patient.

**12.5.2 Episode of Care**

For each patient, a 90-day Run-in-Period prior to the index date will be used to calculate baseline patient baseline covariates. The EIMG Referral Decision Period is the 30 days after the index visit date. The Treatment Period is 120 days from the initial visit date, providing sufficient time for patient referral, entry into and completion of the 12-week PA program. The Outcome Period is the 90 days following the treatment period.

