This multiple case study design will examine the adoption, implementation, and reach of EIMG (i.e., clinic workflow, referral process) across Prisma Health primary care clinics. Twenty Prisma Health primary care clinics will have the opportunity to adopt EIMG beginning in August 2023. Adopting clinics will receive a standardized instructional video and have the EIMG referral process activated, allowing providers to refer eligible patients to the 12-week evidence-informed PA program. In January 2024, adopting clinics will receive an in-depth, tailored EIMG onboard training. At EIMG adopting clinics, we will track referral rates of eligible patients over two phases lasting a total of eight months (months 1-4 after instructional video, months 5-8 after tailored onboard training).

We will use a mixed methods approach to explore factors related to the adoption of EIMG (i.e., characteristics of adopting versus non-adopting clinics), achieving optimal implementation (i.e., clinic workflow, referral process), reach (i.e., proportion of eligible patients receiving a referral, characteristics of referred versus non-referred patients), and patient enrollment in evidence-informed PA programs at participating community PA facilities. The RE-AIM framework will inform the assessment of implementation outcomes, while the i-PARIHS framework will be used to understand contextual factors (i.e., determinants) influencing patient- and clinic-level outcomes. Careful attention will be paid to issues of health equity across all RE-AIM dimensions over the course of the study. Finally, this work will examine the impacts of EIMG implementation on healthcare costs and patient outcomes to assess the cost-effectiveness associated with implementing EIMG in a major health system.

Integrating the EIM model in health systems to connect patients with available community resources has the potential to significantly alter clinical practice and improve population health outcomes. Information gained from this study will lead to the development of a generalizable approach and materials that will inform future implementation strategies on optimizing and scaling up the integration of comprehensive PA models in U.S. health systems. Study findings will also provide cost estimates of potential savings to health systems integrating PA as a population health management tool through clinic-community linkages.

Figure 1. Overall study schematic.

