## 6.0 STUDY DESIGN

### 6.1 Overview of Study Design

This study will employ a single arm, multiple case study design using a mixed methods approach to examine the adoption, implementation, and reach of EIMG across Prisma Health primary care clinics (i.e., clinic workflow, referral process), leading to patient enrollment in a community-based, evidence-informed PA program. Eligible Prisma Health primary care clinics that have not yet received EIMG onboard training and activation will be provided with the opportunity to adopt EIMG as a part of their clinic practice and patient workflow process. A mixed methods approach will examine contextual factors influencing decisions to adopt/not adopt EIMG.

Clinic champions at clinics adopting EIMG will be provided with a brief pre-recorded training video to disseminate to their clinic staff (e.g., physicians, nurses, medical assistants, administrative assistants) on how to provide their patients with an EIMG referral. All providers at the clinic will have the ability to screen and identify physically inactive patients and provide them with an EIMG referral. Initial implementation and reach of EIMG at adopting clinics will be tracked for approximately four months following the dissemination of the pre-recorded training video. After four months, the EIMG team will provide a more in-depth, standardized clinic onboard training following established protocols iteratively developed and refined through the initial addition of EIMG clinics between 2016-19. The onboard training, which consists of an overall presentation of the EIMG program and specific information on placing the referral order and patient workflow, has been adapted for virtual environments due to its notable added benefits, including its recording to serve as an ongoing reference tool for those who cannot attend initial training and incoming staff. Implementation and reach of EIMG will be tracked for an additional four months after the onboard training.

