### **6.2.7 Rationale for Control Condition**

The selection of our control group was influenced by several factors. There are currently only 20 Prisma Health primary care clinics that have not received EIMG onboarding and activation and that are within 15 miles or less of a participating community PA facility. There are no other equivalent Prisma Health primary care clinics to serve as matched controls (i.e., via a stepped wedge design). We are then left with two groups of clinics to serve as controls. The first of these is using a within-clinic design and comparing patient health outcomes before and after the dissemination of the initial EIMG Instructional Video. Secondly, from past experiences, we anticipate that several of the 20 clinics will choose not to adopt EIMG and/or will be non-responsive to our invitation. As one of our study aims, we will evaluate contextual factors and differences between adopting and non-adopting clinics. Clinics that do not adopt EIMG will not be 'activated' and can therefore serve as control clinics, particularly when evaluating patient-level outcomes, as none of their patients will have had the opportunity to participate in EIMG.

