### 12.3 Rationale for Sample Size and Statistical Power

Sample size was established via simulation in R version 4.2.3 (R Core Team, 2023) utilizing preliminary data from clinics participating in a pilot study. This analysis is based on a within clinics, repeated measures design with two levels of EIMG exposure: Instructional Video and Onboard Training. The outcomes (e.g., referral rates) will be measured 4 times (once per month) under each level of EIMG, for a total of 8 observations per outcome per clinic. Two marginal referral rate profiles were considered in determining the sample size: a step effect of

EIMG onboarding with parallel time effect (main effects model) and a step plus accelerated time effect. A generic plot showing the two marginal rate profiles considered is presented in Figure 5.

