$E_{ijk}$  equals 1 if patient “i” in the episode at clinic “j” in the “k-th” month after study initiation was referred to EIMG, 0 otherwise;  $X_{ijk}$  represents patient-specific baseline demographic, clinical, and socioeconomic factors,  $L_j$  are a series of binary variable for each Prisma clinic “j”,  $M_k$  is a count variable representing the number of months since the beginning the study that contains patient “i’s” index date, and  $C_{ijk}$  equals 1 if the episode occurred in a period in which the clinic “j” received or had previously received EIMG activation, 0 otherwise. The parameters  $\omega_j$ ,  $u_k$ , and  $\epsilon_{ijk}$  represent the model random effects associated with site “j”, month “k”, and patient “i”, respectively. We will estimate equation (1) using a generalized linear mixed model. The estimate of parameter  $\beta_4$  equals the effect of standardized EIMG training on the probability of the patient within the episode being referred to EIMG. Variables within  $X_{ijk}$  will include patient history of EIMG use. Our stepped wedge design will enable us to directly control for unmeasured factors associated with site and time. Secondary analyses will assess differences in the impact of standardized EIMG training by stratifying by eligible conditions (i.e., overweight/obese, hypertension, type 2 diabetes).

While EIMG activation will be randomly assigned to clinics using the stepped wedge design, actual EIMG referral decisions will remain at the discretion of provider and patient. As a result, referral decisions for some patients will be “non-compliant” at the clinical level. Providers may refer patients into EIMG based on factors unmeasured by the researcher that are related to study outcomes which can confound estimation of the effect of EIMG on study outcomes. With non-compliance, it is problematic to use “as treated” EIMG referral variation to assess the effects of EIMG referrals on study outcomes. Instrumental variable (IV) methods using randomized EIMG activation as an “instrument” will be used to avoid confounding problems. In this scenario IV estimation will yield consistent estimates of the effect of EIMG referral on study outcomes for the subset of patients whose referrals are responsive to the randomized clinical-level EIMG activation. This is known as the Complier Average Causal Effect (CACE). The CACE model is specified as:

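### Aim 2 episodes run 210 days from the index visit, but no rule says how to code exposure when an episode crosses activation or onboard training

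*Combined protocol and SAP*

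**What the plan says.** Section 12.5.2 builds the Aim 2 episode from the index visit: "The Treatment Period is 120 days from the initial visit date", "The Outcome Period is the 90 days following the treatment period", and, for referral, "The EIMG Referral Decision Period is the 30 days after the index visit date". Section 12.5.5 sums costs over the whole episode and takes health change from the index visit to the first provider visit in the Outcome Period with the measurement.

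The same section defines the instrument C as 1 when the episode fell in a period in which the clinic "received or had previously received EIMG activation, 0 otherwise". Yet the text introducing equation (2), and the later interpretation of β4, describe the same variable as receipt of standardized EIMG training. These are different events: activation comes with the Instructional Video, and the training comes months later.

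Section 6.2.7 names two controls. One is within-clinic, "comparing patient health outcomes before and after the dissemination of the initial EIMG Instructional Video"; the other is clinics that never adopt EIMG.

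Most places give phases of about four months. The Section 2.0 narrative has "months 1-4 after instructional video, months 5-8 after tailored onboard training", Section 6.1 has referrals "tracked for approximately four months following the dissemination of the pre-recorded training video", and Section 12.3 says outcomes "will be measured 4 times (once per month) under each level of EIMG". The synopsis table instead puts training at about three months, and the narrative's dates (August 2023 and January 2024) are about five months apart.

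The only episode exclusion, in Section 12.5.1, concerns a patient's own earlier episode. Nothing in the available text truncates, censors, excludes or recodes an episode that crosses activation or training.

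**The concern.** An episode is assigned to one exposure status, but its cost and outcome windows are longer than a phase. An episode can therefore be coded unexposed while the clinic is free to refer that patient for much of it. Aim 2 contrasts EIMG with standard care, and its results feed the cost-effectiveness ratio in equation (4), so the unexposed group needs to be unexposed over the window in which it is measured.

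The timing of referral, E, adds to the problem. Section 12.5.2 has a 30-day decision window, while Section 12.5.5 codes E for a referral of the patient in the episode. If E counts only 30-day referrals, a patient referred on day 90 is coded not referred while their program participation enters the measured costs and outcomes. If E counts any referral in the episode, some episodes with C = 0 have E = 1.

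**Working it through.** **Episode length.** 120 + 90 = 210 days after index (Section 12.5.2). The plan states no total and no overlap figure, so there is nothing to reproduce first.

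**Case 1: C = activation.** For an index visit b days before activation, days after activation = max(0, 210 − b), and Outcome Period days after activation = min(90, max(0, 210 − b)).

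| b (days before activation) | Episode days after activation | Outcome Period days after activation (of 90) |
|---|---|---|
| 60 | 150 | 90 |
| 120 | 90 | 90 |
| 150 | 60 | 60 |
| 180 | 30 | 30 |
| 210 | 0 | 0 |

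If index visits are spread evenly over the 210 days before activation (an assumption), about 50% of the cost window and 78% of the Outcome Period fall after activation. The look-back length is not stated. With a four-month look-back all pre-activation episodes cross; with 12 months, 210/365 = 58% do.

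**Case 2: C = standardized training.** For an index visit on day d of a video phase of L days, overrun into the training phase = d + 210 − L, smallest at d = 0.

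| Source of L | L (days) | Minimum overrun | Share of episodes crossing |
|---|---|---|---|
| Synopsis table, about 3 months | 91 | 119 | 100% |
| Narrative and Sections 6.1 and 12.3, 4 months | 122 | 88 | 100% |
| 1 August 2023 to 1 January 2024 | 153 | 57 | 100% |

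At L = 122, at least 88 of the 90 Outcome Period days follow training.

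**Illustration of patient-level size (Case 1).** The documents give no figure, so this rests on assumptions: Section 12.3's step profile read as monthly rates of 0.001, 0.004, 0.007, 0.010, then 0.031, 0.034, 0.037, 0.040; those rates applied per visit; visits on days 0, 90 and 180; 30-day months; even index dates; a four-month look-back. Sums ignore repeat referrals.

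- Video-phase episodes, index visit: (0.001 + 0.004 + 0.007 + 0.010)/4 = 0.55%.
- Video-phase episodes, day-90 visit (months 4 to 7): (0.010 + 0.031 + 0.034 + 0.037)/4 = 2.8%. Total by day 120 is about 3.35%, with 2.8/3.35, about 5 in 6, outside the 30-day window.
- Pre-activation episodes, day-90 visit: three quarters fall after activation, in months 1 to 3, at a mean of 0.004, giving 0.3%.
- Pre-activation episodes, day-180 visit (months 3 to 6): (0.007 + 0.010 + 0.031 + 0.034)/4 = 2.05%. Total about 2.35%.

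The day-180 visit is also where this schedule would read the health outcome, so for health only the 0.3% counts. For cost, a day-180 referral leaves 30 episode days.

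**Direction for the instrumental-variable estimate.** If E counts only 30-day referrals, the outcome contrast reflects 3.35 − 0.3 = 3.05 points of referral by day 120 while the first stage records 0.55. Treating all those referrals as equally effective, 3.05/0.55 is about 5.5, which moves the estimate away from zero. If E counts any referral in the episode, later referrals of C = 0 patients are crossover and mainly weaken the first stage.

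**Follow-up.** Section 7.2 places the retrospective extraction at the end of month 8. Counting from activation, that is about 244 days, and 244 − 210 = 34, so only index visits in about the first 34 days have a complete episode. The earliest training-phase episode, on the shortest timeline, ends at day 91 + 210 = 301. None would be complete if this extraction also serves Aim 2.

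**The case against.** Under the explicit definition in Section 12.5.5, C switches on at activation. Video-phase episodes are then already exposed, and their running into training puts nothing into the unexposed group. That is correct, and it is why the second case is conditional on the competing training wording. The plan uses both, so neither can be set aside until C is defined once.

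A reader might infer that no clean unexposed episode exists. The documents do not support that. Section 6.1 plans matched controls from clinics that do not adopt EIMG, and Section 6.2.7 singles these clinics out for patient-level outcomes. Their episodes cannot be affected, nor can episodes indexed 210 or more days before activation. The within-clinic control in Section 6.2.7 remains exposed to the problem.

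The absolute numbers are also small. At planned rates of a few percent, few patients would be referred late, and Section 4.14 reports that only 35.4% of referred patients enrolled. This stands as a limit on the raw contrasts. It protects the instrumental-variable estimate less, because that divides by a referred share that is itself only a few percent.

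Finally, Section 12.5.5 expects discretionary referral and uses instrumental variables for it. That covers E = 1 with C = 0 if E counts the whole episode. It does not cover referrals that affect the outcome but are left out of E. Figure 6 is not shown in the text available here, so a rule drawn there cannot be excluded.

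**Conclusion.** The concern holds as a gap in the definition of exposure for Aim 2. Followed as written, the plan codes some episodes as unexposed although they extend past activation (C = activation), or codes every video-phase episode as unexposed although all of them extend past training (C = training). The calendar overlap is certain under every timeline in the documents.

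What is certain is exposure of the clinic. Bias at patient level needs a later referral, and its size is not established; the percentages above depend on an assumed 90-day visit interval and on applying monthly rates per visit. A reader might also infer that every Aim 2 estimate is pulled toward zero. That fits the raw contrasts, which late referrals in control episodes dilute. It does not fit the instrumental-variable estimate, which can move away from zero if E is limited to 30 days.

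This is a secondary aim, and the primary referral-rate analysis does not use these episodes. The rules should still be fixed before extraction, since otherwise they would be chosen with the data in view.

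**What to change.** - Define C once, as the clinic's activation status at the index date, and align the training wording around equation (2) with it.
- Admit a pre-activation episode as unexposed only if its day 210 falls before that clinic's activation. Index visits from September to December 2022 would qualify: 31 December 2022 + 210 days = 29 July 2023, before August 2023. Code calendar time so that these months have a value, because M_k counts from the start of the study.
- Keep concurrent non-adopting-clinic episodes as controls.
- Set E = 1 for any referral within the Treatment Period, and keep the outcome windows anchored to the index date for everyone. Starting the window at referral would make it depend on E and leave it undefined for non-referred patients.
- Do not interpret video-phase against training-phase episodes as a training contrast on patient outcomes.
- Extract EHR data until at least 210 days after the last included index visit.

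The cost is SAP and extraction wording, an earlier EHR look-back and a later final extraction. The historical control episodes will be older and more open to secular change, which the time term and the concurrent non-adopting clinics address only in part. Some referrals late in the Treatment Period will count as E = 1 with little program time before the outcome is read.

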**Figure 6. Defining the Episode of Care**

**12.5.3 Data Sources**

*Resource Activity Logs:* Prisma employment records by-labor-type (i.e., physician, nurse care coordinator, referral coordinator).

*Patient-Specific Healthcare Resources Used:* For EIMG-eligible patients, we will collect from the Prisma Health Epic EHR during the episode of care:

- 1) All healthcare utilization received by Healthcare Common Procedure Coding System (HCPCS), Diagnosis Related Group (DRG), and National Drug (NDC) codes; and
- 2) REDCap-based provider surveys to assess the resources used by EIMG and the 12-week PA program.

*Resource Unit Price Data:* Medicare standard pricing files for HCPCS, DRG and NDCs, and Prisma average wage rates of Prisma labor resources.

*Patient-Specific Health Outcomes:* From the Prisma Epic EHR we will collect: 1) blood pressure; 2) body weight; 3) hemoglobin A1c; 4) full lipid profiles, and 5) PA levels for each patient at the index visit and across the episode of care.

**12.5.4 EIMG Training Costs Per Eligible Patient**

Analysis will be performed from the perspective of a healthcare system interested in the costs of initiating EIMG across system clinics (i.e., physician nurse care coordinator, referral coordinator) for implementing the EIMG model. Toward this end we will calculate: 1) Total Fixed Cost (TFC) to develop the EIMG implementation toolkit; 2) Total Variable Cost (TVC) of providing the EIMG onboard training and EIMG activation at participating clinics; and (3) number of EIMG eligible-patients (N) over the study period. Retrospective analysis of the Prisma Employment records will be used to estimate the labor hours by labor type used to develop the fixed costs associated with developing the EIMG implementation toolkit (TFC). For the TVC, we will calculate the labor hours by labor type for those performing and attending the standardized EIMG training classes. TFC and TVC will be estimated by multiplying hours by Prisma wage rates by labor type. TFC and TVC will be combined with the number of eligible patients (N) to calculate:

$$(1) \text{ EIMG Training Costs Per Patient} = \frac{TFC+TVC}{N}$$

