$$(3) \quad Y_{ijk} = \alpha_0 + \alpha_1 \cdot X_{ijk} + \alpha_2 \cdot L_j + \alpha_3 \cdot M_k + \alpha_4 \cdot \hat{E}_{ijk} + \rho_j + \tau_k + \vartheta_{ijk}, \text{ where}$$

$\hat{E}_i$  equals the *predicted probability* of that patient “i” is referred to EIMG from equation (2); and the other variables defined as in equation (2). The parameters  $\rho_j$ ,  $\tau_k$ , and  $\vartheta_{ijk}$  represent the random effects associated with site “j”, month “k”, and patient “i”, respectively. The estimated parameter  $\alpha_4$  on  $\hat{E}_{ijk}$  is the CACE or the average treatment effect for patient subset whose EIMG referral was influenced by EIMG activation at the clinic.  $C_{ijk}$  in equation (2) serves as the “instrument” and only the portion of variation in  $\hat{E}_{ijk}$  stemming from  $C_{ijk}$  is used to estimate  $\alpha_4$ . Because  $C_{ijk}$  will be randomly assigned, EIMG referral variation stemming from this assignment will be independent of unmeasured confounding variables. Two-stage least squares (2SLS) IV estimators will be used to estimate the effects of EIMG referrals induced by clinical-level EIMG activation on study outcomes. For each study outcome, equation (2) will serve as the first stage

equation of 2SLS, and second stage model will be equation (3). Because our expected sample sizes will be greater than 500 *our 2SLS estimates will be distributed normally via the central limit theorem regardless of the distribution of the underlying error term.* Each 2SLS model will be estimated with robust standard error methods appropriate for 2SLS models using STATA to account for error structure in equation (3).

Define  $\alpha_{4C}$  as the 2SLS estimate when episode healthcare cost is the dependent variable in equation (3) and  $\alpha_{4H}$  as the 2SLS estimate when a health outcome change is the dependent variable in equation (3). Combining these estimates with the estimates of average patient EIMG training costs from Section F3.2 yields the following cost-effectiveness ratio of EIMG relative to standard care:

$$(4) \text{ EIMG Cost Effectiveness Ratio} = \left[ \frac{(\text{EIMG Training Costs per Patient} + \alpha_{4C})}{\alpha_{4H}} \right]$$

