The ratio in equation (4) equals the incremental cost per patient associated with the EIMG referral induced by clinical-level EIMG activation per average change in health outcome associated with the EIMG referral induced by clinical-level EIMG activation. Separate estimates of equation (4) will be calculated by clinical diagnosis using the health outcome change in the denominator most relevant to the specific diagnosis (e.g., change in hemoglobin A1c for type 2 diabetes).

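### Equation (4) adds a training cost per eligible patient to a cost effect per induced referral, so the training term is too small, by a factor the plan does not fix

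*Combined protocol and SAP*

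**What the plan says.** Section 12.5.4 sets out total fixed cost (TFC) and total variable cost (TVC): "TFC and TVC will be combined with the number of eligible patients (N) to calculate" equation (1), which divides their sum by N, defined as the "number of EIMG eligible-patients (N) over the study period". Section 7.4 identifies eligible patients whether or not they were referred, so equation (1) is a cost per eligible patient.

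Section 12.5.5 then estimates two effects by two-stage least squares (2SLS): α4C for episode healthcare cost and α4H for change in a health outcome. Both are complier average causal effects, stated to apply "for the subset of patients whose referrals are responsive to the randomized clinical-level EIMG activation". The two parts are joined as follows: "Combining these estimates with the estimates of average patient EIMG training costs from Section F3.2 yields the following cost-effectiveness ratio". (The protocol has no Section F3.2; 12.5.4 is presumably meant.) Equation (4) is [training cost per patient + α4C] / α4H, and the plan reads it as the "incremental cost per patient associated with the EIMG referral induced by clinical-level EIMG activation per average change in health outcome".

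The exposure is described in two ways. The first-stage coefficient β4 "equals the effect of standardized EIMG training on the probability of the patient within the episode being referred to EIMG", but the variable it multiplies, C, is 1 when the clinic "received or had previously received EIMG activation, 0 otherwise". Under sections 8.3 and 8.4 activation and onboard training are separate events, months apart.

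**The concern.** The sum in the numerator has two units. The training term is dollars per eligible patient, while α4C is dollars per induced referral. The denominator α4H is also per induced referral, and so is the plan's reading of the result. The qualifier in the title of 12.5.4 is lost when equations (1) and (4) label the term simply as a cost per patient, and nothing in 12.5.4 or 12.5.5 converts one scale to the other.

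Referral is at provider and patient discretion, so induced referrals can be far fewer than eligible patients. Training is paid for whether or not referrals follow, and dividing it over patients who were never referred makes each referral look cheap. Section 5.3 offers the economic evaluation as input to insurers' coverage decisions and health systems' adoption decisions.

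**Working it through.** **Inputs.** T = TFC + TVC and N come from equation (1), β4 from equation (2), and α4C and α4H from equation (3). None has a value in the documents. The plan states no training cost or cost-effectiveness figure, so there is nothing to reproduce and the check is one of units.

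**Step 1: the ratio on one scale.** Let N be the eligible episodes with C = 1, so that induced referrals are R = N × β4.

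- Total incremental cost = T + N × β4 × α4C
- Total health change = N × β4 × α4H
- Ratio = [T/(N × β4) + α4C] / α4H

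Equation (4) has T/N where T/(N × β4) belongs.

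**Step 2: the factor.** (T/R) ÷ (T/N) = N/R, which exceeds 1 whenever 0 < R < N. With N as in step 1 it equals 1/β4. If N also takes in eligible patients seen only while C = 0, as a count over the study period might, N/R is larger than 1/β4.

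**Step 3: illustration of size.** Section 12.3 uses planning referral rates of 0.01 at the end of the video phase and 0.04 at month 8. If β4 lay in that range, the factor would run from 1/0.01 = 100 to 1/0.04 = 25.

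**Step 4: invented example.** Take T = 100,000, N = 10,000, α4C = −200 and α4H = −5 (a fall, as for blood pressure). Equation (4) gives a training term of 100,000/10,000 = 10, a numerator of 10 − 200 = −190 (a saving) and a ratio of −190/−5 = 38. On one scale:

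| β4 | T/(N × β4) | Numerator | Ratio |
|---|---|---|---|
| 0.01 | 1,000 | 800 | −160 |
| 0.02 | 500 | 300 | −60 |
| 0.03 | 333.3 | 133.3 | −26.7 |
| 0.04 | 250 | 50 | −10 |

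Direct calculation from the totals in step 1 gives the same ratios. Every corrected numerator here is a net cost. In general the sign reverses only if T/N < −α4C < T/R.

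**Step 5: patients versus episodes.** N counts patients, whereas equations (2) and (3) use episodes. Section 12.5.2 gives a 120-day Treatment Period and a 90-day Outcome Period, 210 days in all. Section 12.5.1 adds that "candidate episodes will be excluded if the index date is within 90 of the end of a previous care episode for that patient". If that 90 means days and an episode ends with its Outcome Period, a second index visit is possible only after day 210 + 90 = 300, beyond both 8 months (about 244 days) and 9 months (about 274 days). Once both counts are limited to C = 1, patients and episodes coincide, so this is not a second mismatch.

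**Step 6: do the two possible repairs agree?** Version (a) is the ratio in step 1. Version (b) is [T/N + reduced-form cost effect] / reduced-form health effect, where each reduced-form effect is β4 × α4. With one β4 they are identical. But 12.5.5 fits a first stage for each outcome, and health change exists only where an Outcome Period visit recorded it, so the cost and health samples can differ. Keep the example, with β4 = 0.02 in the cost sample and 0.03 in the health sample:

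- (a) with 0.02: (500 − 200)/−5 = −60
- (a) with 0.03: (333.3 − 200)/−5 = −26.7
- (b): (10 − 0.02 × 200)/(−0.03 × 5) = 6/−0.15 = −40

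**The case against.** Training cost per eligible patient is a legitimate quantity, and the title of 12.5.4 names it correctly. That stands, but it belongs beside effects per eligible patient, not beside complier effects.

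The instrumental-variable model may not survive anyway. Section 12.5 assumes randomised stepped-wedge activation, whereas 6.1 and 8.1 describe a single-arm, one-wave design, and 6.1 bases the cost-effectiveness work on matched controls at non-adopting clinics. This also stands: correcting the scale does not validate the instrument. The need for a shared denominator would carry over to any replacement model.

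A reader might infer that the trial will report a false saving. The documents do not support that. Hypothesis 2 predicts lower expenditure for patients who are referred and take part, whereas α4C averages over induced referrals with or without participation. Section 12.5.3 also lists resources used by EIMG and the activity program among patient-level resources; if these enter episode cost, α4C could be positive. The reversal needs a negative α4C inside a window whose limits are unknown.

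A reader might also infer that the whole ratio is wrong by 25 to 100 times. That does not follow. The factor applies to the training term only, and the 12.3 rates are power-calculation inputs, not a forecast of β4.

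**Conclusion.** The mismatch is real and follows from the plan's own definitions. For any positive training cost, the training term in equation (4) is too small by N/R whenever C induces some referrals but fewer than N. The direction is firm; the size is not. The 25 to 100 range assumes β4 of 0.01 to 0.04 and N limited to eligible episodes with C = 1. The effect on the whole ratio, including its sign, cannot be determined from the documents. The primary outcome and Secondary Aim 1 are untouched. It should be fixed before the cost-effectiveness analysis is run.

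**What to change.** Put every term of equation (4) on one denominator, by either route:

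- (a) [(TFC + TVC)/(N × β4) + α4C] / α4H
- (b) [(TFC + TVC)/N + reduced-form cost effect] / reduced-form health effect

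In both, N is the eligible episodes with C = 1 and β4 is the linear 2SLS first-stage coefficient. Section 12.5.5 calls for a generalized linear mixed model in one place and 2SLS in another, so the linear first stage should be named. The versions agree only if the cost and health models share one sample, one covariate set and one first stage. Either fit both on a common sample, or choose one version in advance and, for (a), take β4 from the cost model.

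Also:

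- State whether C marks activation or onboard training, and match TFC + TVC and N to that exposure.
- For the ratios by diagnosis, use N and β4 for each stratum, with a stated rule for allocating TFC + TVC when a patient has several diagnoses.
- Report the number of induced referrals, N × β4, beside the ratio.
- If the instrumental-variable model is replaced, keep training cost on the same denominator as the new cost and health effects.

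The cost is an edit to equations (1) and (4) and to the definitions of N, C and β4. No new data are needed. The downside is a less favourable ratio, and an imprecise one if β4 or the health effect is small.
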